 - Definition of ER: proportion of patients with platelet count higher or equal than 30x10⁹/L and at least doble than baseline at first week (Day 7) from randomisation.
 - Definition of IR: proportion of patients with platelet count higher or equal than 30x10⁹/L in the first month (Day 30) from randomisation.
- To compare the difference of means between study arms of the maximum number of consecutive days with platelet response (CR, R, GR and TR) along the study period. We will evaluate them in the total sample and in the absence of any rescue treatment
- To compare the difference of means between study arms of the total number of days with platelet response (CR, R, GR and TR) along the study period. We will evaluate them in the total sample and in the absence of any rescue treatment.
- To evaluate and to compare the proportion of patients who need rescue treatments and proportion and time to treatment failures.
- To compare the time to loss of response (LoR) in patients who achieved response in both arms.
 - Definition of LoR: number of days from the first time the patient achieved a platelet count ≥30x10⁹/L until platelet count dropped below 30x10⁹/L measured on 2 occasions with more than 1 day apart or presence of bleeding
- To compare the difference between study arms in the proportion of patients requiring any rescue treatment along the study period.
- To compare the difference between study arms in the proportion of patients with adverse events (AEs), including serious adverse events (SAEs) and laboratory safety parameters. AEs will be graded according to National Cancer Institute Common Terminology Criteria for Adverse Events (CTCAE) version 5.0. Bleeding events will be carefully monitored.
- To compare the difference between study arms in the mean change in patients' bleeding from screening to Day 1, Week 8, Week 12, Moth 6, Moth 12andEnd of study Visit (visit 12 months after the last dose of study treatment) assessed with the ITP-bleeding tool in both arm.
- To compare the difference between study arms in the mean change in patients' quality of life from baseline Day 1 (the day of administration of the first dose of study medication) to Week 8, Month 6 (Day 180), Month12 (Day 365) from randomisation and End of study Visit (visit 12 months after

the last dose of study treatment) assessed with SF-36v2, FACIT-F and ITP-PAQ in both arms.

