8. WITHDRAWAL CRITERIA

a. Screening failure

Screening failures are patients who do not fulfill the eligibility criteria for the study, and therefore must not be enrolled and randomised. These patients should have the reason for study withdrawal recorded as "eligibility criteria not fulfilled". This reason for study withdrawal is not valid for randomized patients.

Patients can be rescreened a single time, but they cannot be re-randomized.

b. Reasons for Withdrawal

Patients may withdraw from treatment at any time.

The Investigator may discontinue study treatment for any of the following reasons:

- Patient desires the discontinuation of treatment (i.e., withdraws consent for treatment).
- No response to study treatment.
- Adverse event that, in the opinion of the investigator or the sponsor, contraindicates further dosing.
- Pregnancy or intention to become pregnant.
- Subject noncompliance that, in the opinion of the investigator or sponsor, warrants withdrawal; e.g., refusal to adhere to scheduled visits.
- Noncompliance with study procedures.
- Intercurrent illness or worsening of a chronic condition.

The primary reason for withdrawal from treatment will be documented in the eCRF.

If the reason for withdrawal is an AE, the patient will be followed by the Investigator until such events resolve, stabilize, and, according to the Investigator's judgment, there is no need for further follow-up.

A patient who withdraws consent will always be asked about the reason for withdrawal and the presence of any AE. The Investigator will follow up AEs outside of the clinical study.

If a patient withdraws from participation in the study, then his or her randomization or patient identification number cannot be reused. Withdrawn patients will not be replaced.

Reasons for removal of a subject from the study are:

- Decision by sponsor
- Withdrawal of consent from study
- Death
- Lost to follow-up
- No response treatment failure

c. Handling of Withdrawals

Subjects who are permanently discontinued from receiving study treatment will be followed for safety, including the collection of any protocol-specified information, unless consent is withdrawn or the subject is lost to follow-up. All subjects will be followed for 12 months since randomization, and minimum 6 months after stopping the study treatment (both arms).

The investigator will be requested to collect all patient data until he/she left the study.

d. Lost to follow-up

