- In the DEX arm, if platelet counts are lower than 20x10⁹/L or bleeding symptoms related to thrombocytopenia are present between cycles, rescue therapy with IVIg (maximum dose 2 gr/kg in total during 1 to 5 days) or low doses of prednisone (0,5 mg/kg/d) can be used. If patients use rescue treatment with prednisone, they should be decreased as soon as possible and stopped within 8 weeks.

f. Treatment failure

In the ROM + DEX arm, it would be considered treatment failure if platelets are lower than 30x10⁹/L after 4 weeks with romiplostim at 10 mcg/kg/week or rescue

medication is needed to get this level of platelets despite this dose of 10mcg/kg/week for 4 weeks.

In DEX arm, it would be considered treatment failure if platelets are lower than 30x10⁹/L after 3 cycles of dexamethasone or if rescue medication is needed to get this level of platelets despite the 3 cycles of dexamethasone.

In both arms, treatment failure will be considered to in those patients bleeding who are refractory to therapy in whom it is considered clinically in their best interests to escalate or switch treatment in a way that does not align with the protocol treatment schedules. Patients will be discussed with Steering Committee before to be considered treatment failure.

If patients lose response on the DEX arm, they can be switched from one arm to the other (to TPO-RA), but outside the trial. The treatment will be provided by their centre and this information will be collected up in the CRF. The patients will be considered a treatment failure.

g. Accountability

The study medication (i.e., romiplostim, dexamethasone) will be sent directly from the sponsor to the investigator's site pharmacy preceded by the Regulatory Green Light. The medication is to be used exclusively in the clinical trial according to the instructions of this study protocol.

When a drug shipment is received, the Investigator or designee will check the amount and condition of the delivery, drug expiration date, and sign the Receipt of Shipment Form provided. The Receipt of Shipment Form should be faxed or sent by e-mail to the CRO. The original form will preliminarily be retained at the site and will be collected at the next monitoring visit by the monitor and stored in the TMF at CRO. A copy will remain in the Investigator File at the site. In case of shipment problems, the Investigator or designee shall contact the CRA as soon as possible.

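### Treatment failure is listed as a reason for removal from the study, against the rule that all subjects are followed; the failure definitions also differ between the arms being compared

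*Protocol*

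**What the plan says.** - **Section 8.b, Reasons for Withdrawal**, has two lists. The list of reasons to discontinue study treatment contains "No response to study treatment". The list of reasons for removal from the study contains "No response treatment failure", beside sponsor decision, consent withdrawal, death and loss to follow-up.
- **Section 8.c, Handling of Withdrawals**, keeps subjects who are permanently off study treatment under follow-up "unless consent is withdrawn or the subject is lost to follow-up". It adds: "All subjects will be followed for 12 months since randomization, and minimum 6 months after stopping the study treatment (both arms". It also asks the investigator for data only up to the time the patient leaves the study.
- **Section 9.f, Treatment failure**, defines failure by arm. In ROM+DEX it is platelets below 30x10⁹/L "after 4 weeks with romiplostim at 10 mcg/kg/week or rescue" medication being needed despite that dose. In DEX it is platelets below 30x10⁹/L after three cycles, or that "rescue medication is needed to get this level of platelets despite the 3 cycles of dexamethasone". In both arms, a bleeding patient refractory to therapy who is escalated or switched off protocol also counts, after discussion with the Steering Committee. For DEX only, it adds: "If patients lose response on the DEX arm, they can be switched from one arm to the other (to TPO-RA), but outside the trial". Those patients count as failures, and their later treatment is recorded in the CRF.
- **Section 9.i, Prohibited drugs**, permits the listed drugs once treatment has failed.
- **Section 1.j, Study outcome measures**, compares the "proportion and time to treatment failures" as a secondary outcome.

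**The concern.** Stopping treatment and leaving the study are different events, and 8.b treats failure as grounds for both. Two sites reading the same Protocol could handle the same patient differently: one keeps the visits, the other closes the record. An analysis plan can decide how to treat missing values, but it cannot recover visits that were never made.

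The second issue is the failure endpoint itself. If one arm can meet its rule weeks before the other, and by an additional route, part of any difference in time to failure or in the proportion failing comes from the definition and not from the treatment.

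**Working it through.** **Planned figure used for scale.** Section 11.b gives 63 per arm for 30% against 56.6%, 80% power, two-sided 5% and 15% dropout. With pooled variance and mean rate 0.433:

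n = [1.960·√(2·0.433·0.567) + 0.842·√(0.30·0.70 + 0.566·0.434)]² / 0.266² = 53.3, rounded up to 54 evaluable per arm.

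Then 54 × 1.15 = 62.1, i.e. 63, or 54 / 0.85 = 63.5, i.e. 64. The stated 63 is reproduced closely enough and is not in dispute.

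**1. Does the text contradict itself?**

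| Place | What happens to a failed patient |
|---|---|
| 8.b, first list | May stop study treatment |
| 8.b, second list | May be removed from the study |
| 8.c, follow-up rule | Followed; the only exceptions after stopping treatment are consent withdrawal and loss to follow-up |
| 8.c, last sentence | Data requested until the patient leaves the study |
| 9.f | Treatment after a DEX switch is recorded in the CRF |
| 9.i | Prohibited drugs become allowed, so the patient is still regarded as on study |

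The second row conflicts with the third, fifth and sixth. It cannot be read as meaning treatment discontinuation only, because the first list already covers that.

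**2. Earliest day on which each arm's platelet/rescue rule can be met** (Day 1 = first dexamethasone dose)

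- DEX: three 4-day cycles, spaced 14 to 28 days apart (9.b). Last dose of cycle 3 = 1 + 2 × spacing + 3. At 14 days this is Day 32; at 28 days, Day 60.
- ROM+DEX: start at 3 mcg/kg, weekly steps of 1, maximum 10 (9.b), so seven steps. Romiplostim may start on Day 1 to 4 (6.a). First top dose = 1 + 49 = Day 50, up to 4 + 49 = Day 53. Adding 28 days gives Day 78 to 81.
- Gap: smallest 78 − 60 = 18 days; largest 81 − 32 = 49 days.

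If four weeks were counted only to the fourth top dose, the ROM+DEX rule could be met on Day 71 to 74, still later than the latest DEX day.

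**3. Routes to failure in 9.f**

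| Route | DEX | ROM+DEX |
|---|---|---|
| Low platelets after the stated regimen | yes | yes |
| Rescue needed despite that regimen | yes | yes |
| Refractory bleeding, escalated or switched (no minimum time) | yes | yes |
| Loss of response with switch to TPO-RA outside the trial | yes | not named |

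That is four routes against three.

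**4. Possible data loss.** The Protocol gives no failure rates, so those below are assumptions. With 15% dropout, 63 × 0.85 = 53.6 per arm remain before failures are removed. Observed after failure = 53.6 × (1 − share removed).

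| Removed, DEX / ROM+DEX | DEX left | ROM+DEX left |
|---|---|---|
| 10% / 5% | 48.2 | 50.9 |
| 20% / 10% | 42.8 | 48.2 |
| 40% / 10% | 32.1 | 48.2 |
| 30% / 30% | 37.5 | 37.5 |

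The result runs from a small imbalance to a large one, and to none when the rates are equal. Even then, DEX data could stop sooner.

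**The case against.** The strongest reply is that the Protocol mostly answers the question. Section 8.c follows directly after the bullet and requires follow-up in both arms; 9.f and 9.i agree with it; and 8.b lists possible reasons without ordering every failure to be removed. This stands in part: loss of data is a risk under one reading, not a certainty. It does not remove the contradiction.

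Other parts of the reply stand and limit the point:

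- **Primary endpoint.** A reader might infer that the main comparison is compromised. The documents do not support that. Platelets below 30x10⁹/L, rescue or further ITP therapy generally rule out 6mSROT-50, and the efficacy population in 11.c keeps all randomised and dosed patients in the denominator. The exposed outcomes are secondary, and 11.e calls them exploratory.
- **Loss mainly from DEX.** One might take half of the expected DEX non-achievers as removed: 0.70 × 63 = 44, half = 22 (35%). But the half has no source. The same arithmetic in ROM+DEX gives 0.434 × 63 = 27, half about 14 (22%), and missing 6mSROT-50 is not the same as failing under 9.f: platelets of 30 to 49 without rescue miss the endpoint without meeting the platelet/rescue rule.
- **A failure comparison that favours ROM+DEX by definition.** This is too strong. The refractory-bleeding route applies to both arms and has no minimum time. DEX is given for up to three cycles, so a patient given one or two cannot meet that arm's platelet/rescue rule either. In ROM+DEX, Table 2 escalates weekly while platelets are below 50x10⁹/L, so persistent counts below 30 lead to the top dose unless treatment stops.

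**Conclusion.** The concern holds as a contradiction on follow-up, with a secondary point on comparability. Section 8.b permits removal from the study for failure; 8.c, 9.f and 9.i require or assume continued observation. If 8.b is followed, post-failure data are lost for response at Day 180, Day 365 and end of study, days in response, bleeding, quality of life and resource use. How much is lost, and from which arm, depends on failure rates the Protocol does not give.

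The platelet/rescue rules are reachable 18 to 49 days apart, assuming uninterrupted weekly escalation and three completed DEX cycles, and loss of response with a switch is named as failure only in DEX. That makes the proportion failing and the time to failure hard to interpret between arms, but it does not fix the direction of the result.

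Both parts should be corrected. Neither changes the sample size or undermines the primary analysis.

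**What to change.** 1. In 8.b, delete the treatment-failure bullet from the reasons for removal from the study. Lack of response is already listed as a reason to stop study treatment, so nothing is lost.
2. State in 8.c that patients declared treatment failures stay on the visit schedule and data collection, subject only to the exceptions already given there, and reconcile 8.b with 8.c, 9.f and 9.i.
3. For the between-arm comparison of failure proportion and time to failure, add one analysis definition applied identically in both arms. If it uses a landmark, it must also count failures and switches to non-protocol ITP therapy that occur before the landmark; a definition counting only later events would miss early DEX failures. The arm-specific clinical definitions in 9.f stay as they are.

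The cost is one deleted bullet, one or two sentences and one endpoint definition. The retained visits are those 8.c already requires, and 63 per arm is unchanged.

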In the DEX arm, dexamethasone will be administered 40 mg daily x 4 days for up to 3 cycles every 14 to 28 days.

The use of commercial dexamethasone will be authorized up to 3 days, in case the patient is attended in emergency care while the criteria for the study are being checked and labeled study medication is assigned.

c. Treatment duration and monitoring

The monitoring will be the same in both arms with slight differences to allow for dose adjustments of romiplostim:

In the ROM + DEX arm patients will be reviewed weekly for 8 weeks (56 days). After Week 8, patients will be reviewed every 2 weeks (14 days) for 8 additional weeks and then monthly until Week 52 (Month 12) from randomization.

- o If romiplostim dose should be modified, patients will be reviewed weekly until a stable dose of romiplostim is reached for at least 4 weeks (28 days). After that, patients will go on with visits every 2 weeks (14 days) for 8 weeks and then monthly until Week 52(Month 12) from randomization.
- In the DEX arm, patients will be reviewed weekly until the completion of dexamethasone cycles and for a minimum of 8 weeks (56 days). After that, every 2 weeks (14 days) for 8 additional weeks and then monthly until Week 52 (Month 12) from randomization.

Once romiplostim or dexamethasone is stopped or after 365 days since randomization, patients should be clinically evaluated minimum every 4+/- 1 week for 12 months and continuation of treatment should be decided on an individual basis by the treating physician.

If patient needs treatment again it will be prescribed according to routine clinical practice. In case romiplostim is used, it will not be supported by the sponsor.

d. Criteria for dose adjustments

Dose adjustments for romiplostim will be based on platelet count as described in previous Dosage and administration section.

No dose adjustment for dexamethasone is permitted.

e. Rescue medication

We will consider rescue medication IVIg, platelet transfusion or prednisone. Tranexamic acid will be not considered rescue medication. Rescue medication will be used as follow:

- In the ROM + DEX arm, if platelets counts are lower than 20x10⁹/L or bleeding symptoms related to thrombocytopenia are present between romiplostim doses, rescue therapy with IVIg(maximum dose 2 gr/kg in total during 1 to 5 days) can be used. Prednisolone is not allowed in this arm.

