An Investigational Product Accountability Log will be provided for the trial medication. The record must be continuously updated and contain the dates, quantities and compounds of drugs received, medication identification number(s), the patient identification number to whom the trial medication was dispensed, date and quantity of medication dispense and the initials of the dispenser.

h. Concomitant medication

Throughout the study, investigators may prescribe any concomitant medications or treatments deemed necessary to provide adequate supportive care, except for those listed in section *Prohibited drugs*.

For concomitant therapies therapy name, indication, dose, unit, frequency, route, start date and stop date will be recorded.

Reduction or discontinuation of permitted concurrent ITP therapies may begin once a subject's platelet count has increased to ≥50x10⁹/L.

Rescue medication will also be collected.

Concomitant therapies are to be collected from screening through the EOS visit, as applicable.

i. Prohibited drugs

The following medications are not permitted during this study. After treatment failure, they will be allowed:

- Other thrombopoietic receptor agonists
- Any cytotoxic agents, alkylating agents
- Rituximab
- rHuTPO
- Interferon
- Herbal supplements that are associated with bleeding side effects including, but not limited to, gingko biloba, garlic, ginseng, fish oil, dong quai, feverfew. Garlic and ginseng taken through a normal diet are not excluded.
- Aspirin at doses higher than 100mg or anticoagulant drugs.
- Treatments for ITP other than allowed rescue medications (includings plenectomy).
- Any other investigational agents that are not approved

Should a subject require administration of any of the medications listed above, sponsor should be consulted before the medication is administered, when possible. In all cases, sponsor must be informed within 24 hours. Sponsor may decide that the subjects will be ineligible to receive additional administrations of study medication.

STUDY SCHEDULE AND STUDY FLOW-CHART

Study flow-chart

[figure not shown]

Table 3. Schedule of study assessments.

DEX arm

Visit number	Visit 0 Screening	Visit 1 Baseline	Visit 2- 8	Visit 9	Visit 10, 11, 12, 13 and 15	Visit 17-18	Visit 19	Visit 20-24	Visit 25	Visit 26-36 (Periodical clinical evaluation after the end of study medication ¹¹)	Visit 37 (End of study Visit) ¹²	

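### Section 8.b removes treatment failures from the study, while sections 8.c and 9.c keep them in follow-up

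*Protocol*

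**What the plan says.** Section 8.b of the protocol holds two lists. The first, introduced by "The Investigator may discontinue study treatment for any of the following reasons", concerns study drug and already contains lack of response. The second, introduced by "Reasons for removal of a subject from the study are", concerns participation. It names sponsor decision, consent withdrawal, death, loss to follow-up and "No response treatment failure".

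Section 8.c then deals with subjects who permanently stop study treatment. They "will be followed for safety, including the collection of any protocol-specified information, unless consent is withdrawn or the subject is lost to follow-up". It goes on: "All subjects will be followed for 12 months since randomization, and minimum 6 months after stopping the study treatment (both arms").

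Section 9.c covers the period after romiplostim or dexamethasone is stopped, or after Day 365: "patients should be clinically evaluated minimum every 4+/- 1 week for 12 months". Section 6.a gives 6 months for the same period. Neither section exempts patients who have failed treatment.

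Section 9.f defines failure as a platelet count below 30x10⁹/L despite full study treatment, or rescue needed to reach that level. It adds refractory bleeding that calls for a change of therapy outside the protocol schedule, and DEX-arm patients who lose response and switch to a TPO receptor agonist. For those who switch it says: "The treatment will be provided by their centre and this information will be collected up in the CRF". Section 9.i says of the prohibited drugs: "After treatment failure, they will be allowed".

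**The concern.** Death and loss to follow-up make observation impossible, and consent withdrawal makes it impermissible. Treatment failure does neither: it is an outcome, and the patient can still attend. Listing it as a ground for removal tells the site to stop collecting data because the result was bad, while the next subsection tells it to continue.

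The endpoints at stake are those measured at fixed times or accumulated over the study: CR, R, GR and TR at Day 180 and Day 365, days in response, rescue use, SF-36v2, FACIT-F, ITP-PAQ, ITP-BAT and health resource use. If failures are removed, these are missing in the patients with the worst course, and the missingness depends on the outcome. A statistical analysis plan can choose how to treat the gap but cannot recover platelet counts or questionnaires that were never obtained. With about 30 sites in three countries, uneven practice between sites is foreseeable.

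**Working it through.** The point is a conflict between instructions, so the check sets the texts side by side and then asks which scheduled assessments are exposed. The protocol gives no figure for treatment failures that could be reproduced.

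**1. Can 8.b and 8.c both be obeyed?**
- The 8.b item takes a declared failure out of the study.
- The first 8.c rule keeps a subject who stops treatment under observation, with protocol data collected, and names two exceptions: withdrawn consent and loss to follow-up. Failure is not one of them.
- One could read that rule as covering only people who stop drug and are not removed. The second 8.c rule closes this route, because it applies to all subjects in both arms without qualification.
- A failure removed before the 8.c minimum has been reached therefore breaches that rule.

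**2. Which text is the outlier?**
- 9.c, like 8.c, continues evaluation after stopping and does not carve out failures.
- Lack of response already appears in the treatment-discontinuation list, so the removal item is not needed to let a clinician stop an ineffective drug.

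**3. Which assessments are exposed?** Assume first doses on Day 1, every cycle or dose step on schedule, and the platelet criterion of 9.f.
- DEX arm, third cycle starts: 1 + 2 × 14 = Day 29, or 1 + 2 × 28 = Day 57. Last tablets: Day 32 or Day 60. If failure can be judged the next day, that is Day 33 or Day 61. If the third 28-day interval must also elapse, it is 57 + 28 = Day 85.
- ROM+DEX arm: 3 to 10 mcg/kg in steps of 1 is 7 weekly steps, so 10 mcg/kg is reached on 1 + 7 × 7 = Day 50. Four weekly doses fall on Days 50, 57, 64 and 71, and a week after the last is Day 78.
- Minimum end of follow-up under 8.c, from the last dose: max(365, 32 + 180 = 212), max(365, 60 + 180 = 240) and max(365, 71 + 180 = 251). All three give Day 365.
- Required follow-up lost if removal occurs on these dates: 365 − 33 = 332, 365 − 61 = 304, 365 − 85 = 280 (DEX) and 365 − 78 = 287 days (ROM+DEX).

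All these dates precede Day 180, so in either arm removal at the earliest failure date loses both the Day 180 and the Day 365 assessment. A later failure loses less. The order of the arms depends on how the end of the third cycle is read.

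**4. Effect on the primary endpoint.** 6mSROT-50 needs counts of at least 50x10⁹/L for at least 180 days from cessation, without any ITP treatment and without WHO grade 2 or worse bleeding. A patient who fails on counts below 30x10⁹/L, on need for rescue, or by switching therapy does not meet it. Their status is settled without the later visits.

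**The case against.** The best defence is that 8.c's exceptions are not a complete list. Sponsor decision is also a removal ground in 8.b, does not prevent observation either, and is likewise absent from 8.c. Section 8.c also ends by asking for data up to the time a subject leaves, so it contemplates leavers. That is fair, but it only shows that people may leave. It does not reconcile removal for a poor outcome with follow-up of all subjects.

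Section 9.f requires discussion with the Steering Committee before a patient is considered a failure, so a site may not be free to declare one alone. That controls who is labelled a failure, not what happens to follow-up afterwards.

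The supporting texts are weaker than they look. The CRF sentence in 9.f covers only DEX-arm patients who lose response, and their switch is described as outside the trial. Section 9.i gives a drug permission, not a follow-up rule. Analysis in the total sample is contrasted with analysis without rescue, so it bears on follow-up only by implication. The point therefore rests on 8.b against 8.c and 9.c.

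Three stronger readings may tempt a reader, and the protocol supports none of them.
- That the response difference would be distorted by a calculable amount. No failure rate is given for this trial, the planning rates of 30% and 56.6% belong to the primary endpoint, and efficacy is analysed in all randomised and dosed patients, so removed patients cannot be assumed to leave the denominator.
- That the DEX arm necessarily fails earlier and so loses more data. Day 33 or 61 comes before Day 78, but Day 85 comes after it.
- That safety data would be largely lost. Section 10.c records adverse events only to 30 days after the last dose in any case, and follows recorded events to resolution even in early withdrawals.

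**Conclusion.** The contradiction is real: the removal list in 8.b cannot be squared with 8.c and 9.c for a patient declared a treatment failure. If a site follows 8.b, the fixed-date responses, days in response, rescue use, quality of life, ITP-BAT and resource use become informatively missing in failures. On the scheduling assumptions shown, this can cost up to 280 to 332 days of required observation per patient, with both the Day 180 and Day 365 assessments.

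Neither the size nor the direction of any bias in the treatment comparison can be stated. The number of failures, their split by arm, and how many sites would apply the removal item are all unknown.

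The importance is moderate. The primary comparison is hardly affected provided failures are counted as non-responders, as the endpoint definition implies, and section 11.e declares the secondary results exploratory. It is still worth correcting, because the missing observations cannot be recovered later.

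**What to change.** - Section 8.b: delete treatment failure from the list of reasons for removal from the study. Keep lack of response only in the list of reasons to stop study treatment.
- Section 9.f: add a sentence such as: Patients declared treatment failures remain in the study and are followed under sections 8.c and 9.c.

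The cost is two short edits in a protocol amendment and a letter to sites. No patients, visits or procedures are added, because 8.c already requires the follow-up.
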